8.1.2. QTc Stopping Criteria

- The *same* QT correction formula *must* be used for *each individual participant* to determine eligibility for and discontinuation from the study. This formula may not be changed or substituted once the participant has been enrolled.
 - For example, if a participant is eligible for the protocol based on QTcF, then QTcF must be used for discontinuation of this individual participant as well.
 - Once the QT correction formula has been chosen for a participant's eligibility, the *same formula* must continue to be used for that participant *for all QTc data being collected for data analysis*. Safety ECGs and other non-protocol specified ECGs are an exception.
- A participant that meets the bulleted criterion based on the average of triplicate ECG readings will be withdrawn from study treatment.
 - QTc, QTcB, QTcF >500 msec,
 - Change from baseline: QTcF >60 msec

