	out over multiple days - except as noted in footnotes)	Day –1	Day 1	Day 2	Day 3	Day 4	Day 5	Day 6	Day 7	Day 8	Day 9	Day 10	Day 11 0 h	Day 12 24 h	Day 13 48 h	Day 14 72 h	Day 15 96 h	Day 16 120 h	7-14 days after last dose
24 h Holter Monitoring ⁶	Х																		
Pregnancy Test (females)	X	Х																	Х
Dosing of GSK2838232			Х	Χ	Х	Х	Х	Х	Χ	Χ	Χ	Х	Х						
Plasma PK sampling ⁷			Х	Χ	Χ	Х	Χ	Χ	Χ	Χ	Χ	Χ	Χ	Χ	Х	Χ	Χ	Χ	
Adverse Event Assessment ⁸		Х	Х	Х	Х	Х	Х	Х	Х	Х	Х	Х	Х	Х	Х	Х	Х	Х	Х
Concomitant Medications		Х	Х	Х	Х	Х	Х	Х	Х	Х	Х	Х	Х	Х	Х	Х	Х	Х	Х
Discharge from Unit															X 9				
Out Patient Visit	Х															Χ	Χ	Χ	Χ

BMI = Body Mass Index; ECG = Electrocardiogram; FSH = Follicle Stimulating Hormone; HbsAg = Hepatitis B surface Antigen; HCV = Hepatitis C Virus; Hem/Chem = Hematology/Clinical Chemistry; HIV = Human Immunodeficiency Virus; IP = Investigational Product; PK = Pharmacokinetic(s).

- 1. A single blood pressure (BP) and Heart rate (HR) assessment will be collected at screening and Day -1. On Day 1 triplicate BP and HR will be collected at pre-dose and single assessments at 1, 4, 24, 48 and 72 h (Day 4) post-dose, Day 5, Day 6, Day 7, Day 8, Day 9, Day 10, Day 11 at pre-dose (triplicate), and single assessment at 1, 4, 24, 48 and 72 h post-dose, and at follow-up.
- 2. A single 12-Lead ECG will be collected at screening and Day -1. On Day 1 triplicate 12-Lead ECGs will be collected at pre-dose, and then single 12-Lead ECGs at 1, 4 and 12 h post-dose. Single 12-Lead ECGs will be collected on Days 2, 3, 5, 8. On Day 11 triplicate 12-Lead ECGs will be collected pre-dose, and then single 12-Lead ECGs collected at 1, 4, 12 and 24 h post-dose and at follow-up.
- 3. Echocardiograms must be within 100 days of Day 1.
- 4. Samples for Chemistry and Hematology: Blood samples will be obtained after an 8-hour fast.
- 5. Collect one troponin sample to be analyzed at local laboratory. A second sample will be collected and frozen for potential high sensitivity troponin analysis.
- 6. 24-h Holter monitoring to be performed after confirming negative urine drug screen at screening, and must be within 30 days of Day 1. Holter monitoring on other days only if needed.

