9.4.2. Vital Signs

- Vital signs will be measured in supine position after 10 minutes rest and will include systolic and diastolic blood pressure (BP) and heart rate (HR);
- BP and HR to be taken in triplicate (taken 5 minutes apart) at pre-dose (Part 1: Day 1; Part 2: Day 1 and Day 11) and singular at all other measurement time points;
- If a blood pressure is outside the normal limits (< 90 mmHg or > 160 mmHg), then additional measurements should be taken each minute for 2 more occasions.
- If a HR is outside the normal limits (< 40 bpm or > 100 bpm) then additional measurements should be taken 5 minutes apart for 2 more occasions.
- Ensure correct sized cuff is used for arm circumference.
- It is acceptable that HR be captured from continuous ECG equipment, 12-lead ECG or BP equipment.
- The GSK Medical Monitor should be notified for any clinically significant changes in vital signs.

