9.4.3. Electrocardiograms

- Triplicate 12-lead ECGs will be obtained at least 5 minutes apart in the supine position after 10 minutes of rest pre-dose (Part 1: Day 1; Part 2: Day 1 and Day 11). All values will be recorded.
- Singular 12-lead ECGs will be recorded at all other timepoints using an ECG machine that automatically calculates the HR and measures PR, QRS, QT and QTcF intervals.

- Refer to Section 8.1.2 for QTc withdrawal criteria and additional QTc readings that may be necessary.
- The Investigator will review the 12-lead ECGs. The decision to run repeat measurements if a result is outside of the normal predicted range (and/or considered clinically significant) should be made by the PI based on their clinical judgement to ensure participant safety.

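### Part 2 QTc withdrawal needs a triplicate average, but seven of the eight ECG time points between first and last dose are single and no confirmatory repeat is required before the next dose

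*Protocol*

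**What the plan says.** Protocol 8.1.2 sets two QTc limits, an absolute value above 500 msec and a QTcF rise from baseline above 60 msec. It then states: "A participant that meets the bulleted criterion based on the average of triplicate ECG readings will be withdrawn from study treatment". Withdrawal is mandatory once the criterion is met, and the criterion is defined on the mean of three tracings.

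For Part 2, Protocol 9.4.3 schedules triplicates only before dosing on Day 1 and Day 11. Otherwise, "Singular 12-lead ECGs will be recorded at all other timepoints". Footnote 2 to Table 3 agrees. For the first dosing day it reads: "On Day 1 triplicate 12-Lead ECGs will be collected at pre-dose, and then single 12-Lead ECGs at 1, 4 and 12 h post-dose". The same footnote gives one tracing on each of the four intermediate ECG days (2, 3, 5 and 8), and its only other triplicate is the one before the final dose.

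On confirmation, 9.4.3 says: "Refer to Section 8.1.2 for QTc withdrawal criteria and additional QTc readings that may be necessary". Section 8.1.2 contains no text on additional readings. The sentence in 9.4.3 on repeating an abnormal ECG ends: "and/or considered clinically significant) should be made by the PI based on their clinical judgement to ensure participant safety". It gives no trigger value, number of repeats or time limit. Temporary discontinuation (8.1.3) and dose modification (7.2) are both marked as not applicable. The SAP reproduces the same schedule and adds no confirmatory rule.

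**The concern.** The stopping rule and the ECG schedule do not meet. The rule needs three tracings, and nearly all on-treatment time points supply one. Suppose a Part 2 participant has a single QTcF more than 60 msec above baseline on Day 3. That reading does not meet the mandatory criterion, and nothing obliges anyone to obtain the tracings that would test it before the Day 4 dose. Whether dosing continues rests on individual judgement and not on the stated limit.

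This matters because Protocol 3.3.3 acknowledges that cardiovascular events have been observed and relies on cardiovascular stopping criteria to reduce the risk. The QTc rule is the only cardiac criterion in Section 8.1. Part 2 participants are healthy, expect no benefit, and receive what 5.5 calls the highest practical once-daily dose.

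**Working it through.** The plan gives no figure of its own here, so the check is a count from Table 3 footnote 2 and Protocol 9.4.3, with dosing on Days 1 to 11 (Table 5).

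**ECG time points after the first dose and before the last**

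- Day 1 at 1, 4 and 12 h: 3 single
- Days 2, 3, 5 and 8: 4 single
- Day 11 pre-dose: 1 triplicate

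Total 3 + 4 + 1 = 8, of which 3 + 4 = 7 are single. The Day 1 triplicate precedes any drug. The Day 11 ECGs at 1, 4, 12 and 24 h and the follow-up ECG are single and come after the last dose. Counting those as well, 12 of 13 time points after the first dose are single.

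**Where the one triplicate falls**

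By Day 11 pre-dose, 10 of 11 doses have been given. On scheduled ECGs alone, the rule can prevent only the final dose.

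**Doses scheduled between each single ECG and the Day 11 triplicate**

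The time of the Day 2, 3, 5 and 8 ECGs relative to that day's dose is not stated, so both cases are shown.

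| Single ECG | If before that day's dose | If after it |
|---|---|---|
| Day 1 post-dose | – | Days 2–10: 9 |
| Day 2 | Days 2–10: 9 | Days 3–10: 8 |
| Day 3 | Days 3–10: 8 | Days 4–10: 7 |
| Day 5 | Days 5–10: 6 | Days 6–10: 5 |
| Day 8 | Days 8–10: 3 | Days 9–10: 2 |

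These are ceilings. They assume no repeat and no withdrawal at the investigator's discretion. After a Day 8 reading, no ECG of any kind is scheduled until Day 11 pre-dose, while two or three doses are given.

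**Effect of a mandatory confirmatory rule**

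All 8 time points could then lead to the rule being applied, against 1 of 8 on the present schedule. Scheduled tracings in this window stay at 7 × 1 + 1 × 3 = 10, plus repeats for flagged readings only. Triplicates at every time point would take 8 × 3 = 24.

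**Part 1 for comparison**

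All post-dose ECGs are single: 8 per period on the Table 2 grid, or 9 by its footnote 4, which adds 72 h. Each period has one GSK2838232 dose, at least 10 days of washout follow, and a triplicate precedes the next GSK2838232 dose. The consequence there is small.

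**The case against.** The strongest reply is that the rule does work through unscheduled ECGs. Section 8.1.2 does not confine the triplicate to scheduled tracings and itself mentions safety ECGs outside the protocol schedule. Read with the pointer in 9.4.3, the natural meaning is that further tracings are taken until there are three. This stands in part. A reader might infer that the rule cannot operate in Part 2 before Day 11, and the documents do not support that: a discretionary triplicate would satisfy 8.1.2. But the pointer leads to no text. An investigator who took one repeat, or repeated the ECG after the next dose, would comply with 9.4.3 and leave the rule untested.

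Second, discretion is well supported. The investigator reviews the ECGs, participants stay in the unit until the morning of Day 13, QTcF above 450 msec is excluded at screening, and 8.2 allows withdrawal for safety at any time. Appendix 4 grades a QTc above 0.50 seconds as Grade 3 (by Bazett's formula), and SAP 14.8.2 lists a rise above 60 msec as potentially clinically important. A reader might therefore take the nine-dose figure as an expected exposure. It is not: it requires a physician to pass over a severe-grade or flagged reading and four later single ECGs.

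Third, the heart-rate rule in 9.4.2 ("then additional measurements should be taken 5 minutes apart for 2 more occasions") is a weak precedent, since it is worded as advice, holds no dose and feeds no stopping rule. That is fair. It shows only that the protocol fixes a trigger, number and interval elsewhere.

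Finally, earlier repeat dosing at 200 mg with RTV for 11 days (5.5) is some reassurance. It does not support a numerical exposure bound for 500 mg unboosted, because the RTV ratios in 3.2.1 come from 10 mg and 20 mg doses.

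**Conclusion.** The concern holds as a missing mandatory trigger and deadline. In Part 2, a single QTc reading over a stopping limit neither meets 8.1.2 nor compels a confirmatory triplicate before the next daily dose. On scheduled ECGs the rule can first be tested after 10 of 11 doses. The count of seven in eight is exact and does not depend on when the ECGs are taken relative to dosing.

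The size is modest. About six participants receive active drug in Part 2, discretionary repeats are likely, and no endpoint or estimate changes. The change should still be made, because a mandatory safety rule in healthy volunteers should not depend on discretion to become testable, and the remedy is cheap.

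**What to change.** Add to 8.1.2, with cross-references in 9.4.3 and the Table 3 ECG footnote:

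- In Part 2, any single on-treatment QTc above 500 msec, or QTcF more than 60 msec above the mean of the Day 1 pre-dose triplicate, triggers two further ECGs about 5 minutes apart.
- The repeats use the same correction formula and are completed before any further dose. The formula needs stating because 8.1.2 exempts unscheduled safety ECGs from its consistency requirement.
- The stopping rule is applied to the mean of the three tracings.

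In Part 2 this baseline fits both Protocol 10.3 and the replicate-mean ECG baseline in SAP 5.2, since no study treatment precedes it. If the rule is extended to Part 1, measure the change from the last value before the first RTV dose. Protocol 10.3 takes baseline before the first study treatment, and Section 7 counts RTV as study treatment. The Part 1 Day 1 triplicate follows two RTV doses and could hide an RTV effect on QTc.

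The cost is one protocol amendment and a few extra ECGs in the rare participants who cross a limit. It adds no participants or visits. Repeats before the next dose are feasible because Part 2 participants are in the unit throughout dosing.

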8.1.3. Temporary Discontinuation

Not applicable.

8.1.4. Rechallenge

Not applicable.

8.2. Withdrawal from the Study

- A participant may withdraw from the study at any time at his/her own request, or may be withdrawn at any time at the discretion of the Investigator for safety, behavioral, compliance or administrative reasons.
- If the participant withdraws consent for disclosure of future information, the sponsor may retain and continue to use any data collected before such a withdrawal of consent.
- If a participant withdraws from the study, he/she may request destruction of any samples collected and not tested, and the Investigator must document this in the site study records.
- Refer to the Schedule of Assessments (Table 2 and Table 3) for data to be collected at the time of study discontinuation and follow-up and for any further evaluations that need to be completed.

8.3. Lost to Follow Up

A participant will be considered lost to follow-up if he or she repeatedly fails to return for scheduled visits and is unable to be contacted by the study site.

The following actions must be taken if a participant fails to return to the clinic for a required study visit:

- The site must attempt to contact the participant and reschedule the missed visit as soon as possible and counsel the participant on the importance of maintaining the assigned visit schedule and ascertain whether or not the participant wishes to and/or should continue in the study.
- Before a participant is deemed lost to follow up, the Investigator or designee must make every effort to regain contact with the participant (where possible, 3 telephone calls and, if necessary, a certified letter to the participant's last known mailing address or local equivalent methods). These contact attempts should be documented in the participant's medical record.
- Should the participant continue to be unreachable, he/she will be considered to have withdrawn from the study with a primary reason of lost to follow-up.

9. STUDY ASSESSMENTS AND PROCEDURES

Each participant will have adequate time to provide informed consent of his or her own free will and before conducting any study procedures according to the International Conference on Harmonization (ICH) and Code of Federal Regulations (CFR) guidelines. Each participant will be provided a copy of the signed informed consent document (ICF) before the initiation of any study procedures.

After a participant has provided written informed consent and within 30 days of the first dose of study treatment, the Investigator or other study personnel will determine if the participant is eligible for enrolment in the study. This will be done by reviewing the inclusion and exclusion criteria and completing all of the screening assessments outlined in the Schedule of assessments Tables (Table 2 and Table 3). Screening assessments may be carried out over more than 1 day provided that all required assessments are completed within 30 days before the first administration of study treatment.

Protocol waivers or exemptions are not allowed with the exception of immediate safety concerns. Therefore, adherence to the study design requirements, including those specified in the Schedule of Assessments Tables (Table 2 and Table 3), are essential and required for study conduct.

Whenever vital signs, 12-lead ECGs and blood draws are scheduled for the same nominal time, the assessments should occur in the following order:

- 1. 12-lead ECG.
- 2. Vital signs.
- 3. Blood draws.

Note: The timing of the assessments should allow the blood draw to occur at the exact nominal time. In the event that the timing for a scheduled assessment conflicts with an

assessment that has to be repeated, the scheduled assessment will be performed on time/as scheduled and the repeat assessments will be conducted when feasible.

The timing and number of planned study assessments, including: safety and PK assessments may be altered during the course of the study based on newly available data (e.g., to obtain data closer to the time of peak plasma concentrations) to ensure appropriate monitoring.

The Institutional Review Board (IRB) will be informed of any safety issues that require alteration of the safety monitoring scheme or amendment of the Informed Consent Form.

The timing of planned study assessments is listed in the Schedule of Assessments Tables (Table 2 and Table 3).

9.1. Efficacy Assessments

Not applicable.

9.2. Adverse Events

The definitions of an AE or SAE can be found in Section 12.5, Appendix 5.

The Investigator and any designees are responsible for detecting, documenting, and reporting events that meet the definition of an AE or SAE and remain responsible for following up AEs that are serious, considered related to the study treatment or the study, or that caused the participant to discontinue the study treatment or study (see Section 8). In addition, all ventricular tachyarrhythmias are considered AEs of interest and should be reported to the Sponsor within 24 hours.

9.2.1. Time Period and Frequency for Collecting Adverse Event and Serious Adverse Event Information

- All SAEs will be collected from the signing of the ICF until the follow-up visit at the time points specified in the Schedule of Assessments Tables (Table 2 and Table 3).
- All AEs will be collected from the start of treatment until the follow-up visit at the time points specified in the Schedule of Assessments Tables (Table 2 and Table 3).
- The Sponsor will inform FDA within 7 days of any grade 2 or higher "alteration in personality-behavior or in mood" or "altered mental status" adverse events that occur in participants who have received GSK2838232.
- Medical occurrences that begin before the start of study treatment but after obtaining informed consent will be recorded on the Medical History/Current Medical Conditions section of the case report form (CRF) not the AE section.
- All SAEs will be recorded and reported to the sponsor or designee within 24 hours, as indicated in Section 12.5, Appendix 5. The Investigator will submit any updated SAE data to the sponsor within 24 hours of it being available.

- Investigators are not obligated to actively seek AEs or SAEs in former study participants. However, if the Investigator learns of any SAE, including a death, at any time after a participant has been discharged from the study, and he/she considers the event to be reasonably related to the study treatment or study participation, the Investigator must promptly notify the sponsor.
- NOTE: The method of recording, evaluating, and assessing causality of AEs and SAEs and the procedures for completing and transmitting SAE reports are provided in Section 12.5, Appendix 5.

9.2.2. Method of Detecting AEs and SAEs

Care will be taken not to introduce bias when detecting AEs and/or SAEs. Open-ended and nonleading verbal questioning of the participant is the preferred method to inquire about AE occurrence. Appropriate questions include:

- "How are you feeling?"
- "Have you had any (other) medical problems since your last visit/contact?"
- "Have you taken any new medicines, other than those provided in this study, since your last visit/contact?"

9.2.3. Follow-up of AEs and SAEs

After the initial AE/SAE report, the Investigator is required to proactively follow each participant at subsequent visits/contacts. All SAEs and nonserious AEs of special interest (as defined in Section 3.3.1), will be followed until the event is resolved, stabilized, otherwise explained, or the participant is lost to follow-up (as defined in Section 8.3). Further information on follow-up procedures is given in Section 12.5, Appendix 5.

9.2.4. Regulatory Reporting Requirements for SAEs

- Prompt notification by the Investigator to the sponsor of a SAE is essential so that legal obligations and ethical responsibilities towards the safety of participants and the safety of a study treatment under clinical investigation are met. In addition, all ventricular tachyarrhythmias are considered AEs of interest and should be reported to the Sponsor within 24 hours.
- The sponsor has a legal responsibility to notify both the local regulatory authority and other regulatory agencies about the safety of a study treatment under clinical investigation. The sponsor will comply with country-specific regulatory requirements relating to safety reporting to the regulatory authority, IRB/Independent Ethics Committees (IEC), and Investigators.
- Investigator safety reports must be prepared for suspected unexpected serious adverse reactions (SUSAR) according to local regulatory requirements and sponsor policy and forwarded to Investigators as necessary.
- An Investigator who receives an Investigator safety report describing a SAE or other specific safety information e.g., summary or listing of SAE) from the

sponsor will review and then file it along with the Investigator's Brochure and will notify the IRB/IEC, if appropriate according to local requirements.

• Please see the SRM for SAE reporting contact details.

9.2.5. Pregnancy

- Details of all pregnancies in female participants and female partners of male participants will be collected after the start of study treatment and until the final follow-up visit.
- If a pregnancy is reported, the Investigator should inform GSK within 24 hours of learning of the pregnancy and should follow the procedures outlined in Section 12.6, Appendix 6.
- Abnormal pregnancy outcomes (e.g., spontaneous abortion, fetal death, stillbirth, congenital anomalies, ectopic pregnancy) are considered SAE.

